## Annotation:

1. Inclusion/Exclusion review: every subject needs to meet all inclusion and exclusion criteria. The eligibility checklist needs to be signed by the investigator or sub-investigator.
2. Demographics: includes age, gender, race, and ethnicity.
3. Pre-existing conditions and medical history: obtained from interview or available information and including timing of exposure and onset of symptoms suggestive of SARS-CoV-2 infection.
4. NIAID ordinal scale to be completed daily through Day 28 or 14 days after last dose. This information can be collected from questionnaire; reported events; or directly from the patient.
5. Prior treatments within last 30 days.
6. Physical exam (PE): Full physical exam should be done at screening visit. For the subsequent visits, symptom directed PE can be done per investigator's discretion. If the result is clinically significant, the PE result should be recorded in eCRF.
7. Vital sign: documentation of hospital-based exam is acceptable. Vital signs include body temperature, pulse rate, systolic and diastolic blood pressure, respiratory rate. For screening visit, SpO2, and supplemental oxygen flow rate, FiO2 if known and method of delivery if applicable, also need to be recorded. Record blood pressure and SpO2 while subject is at rest.
8. Nasopharyngeal (NP) swabs: Only NP swab sample is acceptable. The method of taking samples should be consistent for each subject during the whole period of this study. This does not need to be the same before screening visit, when the subject is first time confirmed SARS-CoV-2 positive at local laboratory and/or Point of Care testing. Sample for first positive test must be collected within 3 days prior to start of dosing. Local laboratory and/or Point of Care testing are acceptable.
9. Randomization: randomization should be via the Interactive Voice/Web (IxRS) Response System. Randomization should be done after confirmation the subject meets all inclusion/exclusion criteria. Drugs and Diary Dispense should occur after randomization. It is allowed for the subject to take the drug on the

same day of the screening visit after confirmation of eligibility and randomization (the screening visit is counted as D1 too). The Subject Diary should start to be completed.

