### 5.2 Inclusion Criteria

Subjects are eligible to be included in the study only if all the following criteria apply:

1. The subject or legally authorized representative give signed informed consent which includes compliance with the requirements and restrictions listed in the ICF and in this protocol.
2. Understand and agree to comply with planned study procedures.
3. Male and non-pregnant female subjects with age  $\geq 18$  years of age at the time of randomization.
4. Are currently not hospitalized.
5. Have one or more COVID-19-related symptoms within 5 days of symptoms onset ((FDA COVID-19-Related symptom guidance, See Appendix 2, available at: <https://www.fda.gov/media/142143/download>)
6. Must have first positive SARS-CoV-2 viral infection determination (has laboratory-confirmed SARS-CoV-2 infection as determined by PCR, or other commercial or public health assay in any specimen)  $\leq 3$  days prior to start of the first dose.
7. Women of child-bearing potential, defined as all women physiologically capable of becoming pregnant, unless they are using highly effective contraception, as shown below, throughout the study and for 3 months after stopping GT0918 treatment. Highly effective contraception methods include:
  - Total Abstinence (when this is in line with the preferred and usual lifestyle of the patient. Periodic abstinence (e.g. calendar, ovulation, symptothermal, post-ovulation methods) and withdrawal are not acceptable methods of contraception, or
  - Use of one of the following combinations (a+b or a+c or b+c):
    - a: Use of oral, injected or implanted hormonal methods of contraception or other forms of hormonal contraception that have comparable efficacy (failure rate  $< 1\%$ ), for example hormone vaginal ring or transdermal hormone contraception.
    - b: Placement of an intrauterine device (IUD) or intrauterine system (IUS);
    - c: Barrier methods of contraception: Condom or Occlusive cap (diaphragm or cervical/vault caps) with spermicidal foam/gel/film/cream/vaginal suppository;

- Female sterilization (have had prior surgical bilateral oophorectomy with or without hysterectomy) or tubal ligation at least six weeks before taking study treatment. In case of oophorectomy alone, only when the reproductive status of the woman has been confirmed by follow-up hormone level assessment;

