4.5 Analysis Sets

The Intent-to-Treat Analysis Set (ITT) includes all randomized subjects.

The Modified Intent-to-Treat Analysis Set (mITT) includes all randomized subjects who have received at least one dose of study medication. The primary efficacy analysis will be conducted on the mITT Analysis Set.

The Safety Analysis Set (SS) includes all subjects with at least one dose of study medication and will be analyzed as treated. The disposition, study summary, and safety analysis will be conducted on Safety Analysis Set.

The Per-Protocol Analysis Set (PP) includes all mITT subjects without major protocol violations which will be defined under classification specification prior to unblinding of the study treatment code.

The Pharmacokinetic Analyses (PK) will be conducted on data from at least 200 subjects who receive intervention and have evaluable PK.

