4.10.3 Secondary Efficacy Variables

Hospitalization Percentage

Hospitalization percentage is defined as the percentage of subjects who experience any of the following events due to all causes by Day 28:

- Hospitalization for \geq 24 hours or
- Supplemental oxygen for \geq 24 hours in response to $\text{SpO}_2 \leq 93\%$ or
- Death

The same process used for the primary endpoint analysis will be used to compare the difference between treatment groups.

The following sensitivity analysis for hospitalization percentage will be performed among subset of mITT subjects:

- With dosing days > 7 days;
- With one or several major risk factors below:
 - Single risk factor: age (≥ 50 years; ≥ 60 years), major underlying medical conditions (overweight, obesity, hypertension, diabetes, smoking);
 - Combination of age factor in column 1 and other major underlying medical conditions in column 2 in the table below (e.g., age ≥ 50 years and/or obesity at randomization; age ≥ 60 years and/or obesity at randomization);

Age	Major underlying medical conditions
≥ 50 years	Overweight
≥ 60 years	Obesity Hypertension Diabetes Smoking

- With aged ≥ 50 years and days from symptom onset to study randomization ≤ 5 days and days from the positive SARS-CoV-2 Prior to first dosing ≤ 3 days;
- With aged ≥ 50 years and higher than normal biomarkers (CRP, Ferritin, D-dimer).

All sensitivity analyses will be conducted using one-sided CMH chi-square tests used for the primary endpoint analysis. Forest plots for the sensitivity analysis will be presented.

Change from Baseline to Days 3, 7, 14 and 28 in SARS CoV-2 Viral Load

Change of SARS-CoV-2 viral load from baseline, which will be evaluated in log base 10 scale, will be summarized, and plotted by treatment group and listed. Two sample t-tests will be used to compare differences in the change of SARS-CoV-2 viral load between treatment groups at Day 3, 7, 14 and 28, respectively.

Also, an analysis of covariance (ANCOVA) model will be used to compare the change from baseline in SARS-CoV-2 viral load at Day 3 with fixed effects for treatment group, age and stratification factors (sex, race and ethnicity, and number of risk factors), and baseline viral load as a covariate. If systematic pattern is identified from the residual of predicted values, a transformation of the baseline viral load will be employed to improve the performance of the model. Estimated treatment differences

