Time to sustained 100% SARS-CoV-2 viral reduction (in days) is defined as:

Date when sustained 100% SARS CoV-2 viral reduction is changed to 'Yes' - first dosing date + 1.

If a patient has not experienced SARS-CoV-2 clearance by completion or early discontinuation of study/study treatment, the patient will be censored at the date of their last visit during the post-treatment period.

Time to sustained 100% SARS CoV-2 viral reduction and will be summarized and plotted by treatment group with mITT set using the Kaplan-Meier (KM) method. The 2-sided 95% CIs for the 25th, 50th and 75th percentiles, as well as at days 3, 7, 14 and 28 using the Brookmeyer and Crowley method will be reported when estimable. P-value will be obtained from the log-rank test stratified by age, and sex, race and ethnicity, and number of risk factors at randomization. Hazard ratios and corresponding 95% confidence intervals will be obtained from a Cox proportional hazard model which treated treatment group as a unique covariate, and age, and sex, race and ethnicity, and number

of risk factors as stratas. The Cox proportional hazard model will be also performed by subgroup of duration since symptom onset to randomization category (≤ 3 days; > 3 days).

SARS CoV-2 Viral Clearance

SARS-CoV-2 Viral clearance (Yes/No) is defined when at least two consecutive negative tests proceed a positive test with all tests ≥ 24 hours apart. The date of viral clearance is defined as the earliest date between the consecutive negative tests.

The proportion of subjects that achieve SARS-CoV-2 clearance at Days 3, 7, 14, and 28 will be summarized by treatment in frequency tables, plotted and listed. Viral clearance can only be achieved (Yes) at days with a negative result. Generalized estimating equation (GEE) model will be used to model the proportions of achieving SARS-CoV-2 clearance at different visits. The model will consider treatment group, visit, treatment-by-visit interaction, age and stratification factors (sex, race and ethnicity, and number of risk factors) as fixed effects, and subject as a random effect. Comparisons of GT0918 to placebo for odds ratios (ORs), corresponding 95% CIs and p-values will be calculated at each visit.

Time to SARS-CoV-2 Clearance

Time to SARS-CoV-2 clearance (in days) is defined as:

Date when SARS-CoV-2 clearance status is changed to 'Yes' - first dosing date + 1.

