6.3 Clinical Laboratory Parameters**Table 5 Clinical Laboratory Parameters**

Test category	Local/Central	Test Name
Hematology	Local	Hemoglobin Hematocrit Erythrocyte count (RBCs - Red Blood Cells) Leukocytes (WBCs - White Blood Cells) Differential Neutrophils, segmented Lymphocytes Monocytes Eosinophils Basophils Platelets
Clinical Chemistry	Local	Sodium Potassium Chloride Bicarbonate Total bilirubin Direct bilirubin Alkaline phosphatase (ALP) Alanine aminotransferase (ALT) Aspartate aminotransferase (AST) Gamma-glutamyl transferase (GGT) Blood urea nitrogen (BUN) Creatinine Creatine kinase (CK) Uric acid Total protein Albumin Calcium Phosphorus Glucose Amylase Lipase Lactate dehydrogenase (LDH)
Coagulation	Local	International normalized ratio (INR), partial thromboplastin time: non-activated (PTT) or activated (aPTT)
Additional tests	Local/Central*	C-reactive protein (CRP); high-sensitivity Ferritin D-dimer Procalcitonin Troponin (preferably Troponin I)

Parexel International

Suzhou Kintor Pharmaceuticals, Inc.
GT0918-US-3001

Statistical Analysis Plan

Test category	Local/Central	Test Name
Virology	Central	SARS-CoV-2 viral infection determination at screening - local SARS-CoV-2 viral load test (quantitative ddPCR) - central
Pharmacokinetic Analyses	Central	Analyzed using validated LC-MS/MS methods with a LLOQ of approximately 5.00 ng/mL for GT0918
Hormones (Male &Female)	Central	Testosterone
Hormones (Female)	Local	Serum Pregnancy Urine Pregnancy

* Central laboratories will be used when it can't be tested on local laboratory.

6.4 Subject Questionnaire1. What was the severity of your stuffy or runny nose at its worst over the last 24 hours?

None =0	Mild =1	Moderate =2	Severe =3
------------	------------	----------------	--------------

2. What was the severity of your sore throat at its worst over the last 24 hours?

None =0	Mild =1	Moderate =2	Severe =3
------------	------------	----------------	--------------

3. What was the severity of your shortness of breath (difficulty breathing) at its worst over the last 24 hours?

None =0	Mild =1	Moderate =2	Severe =3
------------	------------	----------------	--------------

4. What was the severity of your cough at its worst over the last 24 hours?

None =0	Mild =1	Moderate =2	Severe =3
------------	------------	----------------	--------------

5. What was the severity of your Low energy or tiredness at its worst over the last 24 hours?

None =0	Mild =1	Moderate =2	Severe =3

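### Viral clearance does not name its qualifying positive test, and time to clearance runs on mITT without requiring a detectable central baseline swab

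*SAP*

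**What the plan says.** **Entry.** Protocol 5.2, criterion 6, accepts "laboratory-confirmed SARS-CoV-2 infection as determined by PCR, or other commercial or public health assay in any specimen", with the first positive no more than 3 days before the first dose. Annotation 8 to the Schedule of Activities adds that "Local laboratory and/or Point of Care testing are acceptable". On keeping the sampling method consistent within a subject, it says "This does not need to be the same before screening visit, when the subject is first time confirmed SARS-CoV-2 positive at local laboratory".

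**Measurement.** The viral endpoints come from another test, listed in SAP 6.3, Table 5, as "SARS-CoV-2 viral load test (quantitative ddPCR) - central". Study swabs must be nasopharyngeal. SAP 4.2 takes as baseline the last pre-treatment value, with no condition that virus be detectable.

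**Definition.** SAP 4.10.3: clearance "is defined when at least two consecutive negative tests proceed a positive test with all tests" at least 24 hours apart. It is dated to the earliest of the consecutive negatives. Time to clearance is that date minus the first dosing date plus 1, and subjects who do not clear are censored at their last post-treatment-period visit.

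**Analysis set.** SAP 4.5 defines ITT, mITT, safety, per-protocol and PK sets only; mITT "includes all randomized subjects who have received at least one dose of study medication". Time to sustained 100% reduction "will be summarized and plotted by treatment group with mITT set using the Kaplan-Meier (KM) method", and time to clearance borrows the same methods. The subgroup list in SAP 4.10.1.3 has no baseline viral load category.

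**Other viral endpoints.** "Change of SARS-CoV-2 viral load from baseline, which will be evaluated in log base 10 scale" is compared by two-sample t-tests at Days 3, 7, 14 and 28, by ANCOVA at Day 3 and by MMRM; the two models carry baseline viral load as a covariate. Percent reduction divides by the baseline load. AUC uses only values above the LoQ of 59.9 copies/mL and is not computed when the Day 1 pre-dose value is missing.

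**The concern.** The test that admits a subject and the test that measures the viral endpoints differ in assay, possibly in specimen, and by up to 3 days. Some subjects may therefore enter with a local positive and have nothing measurable on the central baseline swab. The SAP gives no rule for them.

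Two things are at stake. The first is reproducibility: the definition supports two readings that put the same subject at opposite ends of the time-to-clearance curve, so two programmers could draw different curves from the same data. The second is sensitivity: a subject with no measurable virus at entry, and none later, cannot show an antiviral effect. Keeping such subjects pulls the arms together on the endpoints that most directly test the drug's proposed mechanism.

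**Working it through.** **The plan's own figure.** No sample size or power is stated for any viral endpoint. The only design figure is 668 subjects for the primary endpoint (97% v 91%, one-sided 0.025, about 90% power). A two-proportion calculation gives 328 per arm, 656 in total, or 658 after the O'Brien–Fleming-type inflation of 1.0034. That agrees with 668 to within 3%. It is used below only to fix 334 per arm.

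**Inputs not in the documents.** The share q with an undetectable central baseline is assumed to be 5–20%. Clearance rates are illustrative. These subjects are taken to stay negative throughout; one who turned positive on a later central swab could still clear.

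**Step 1: how such a subject is scored.**
- If the positive must be a central result, no event is possible and the subject is censored at the last visit.
- If the local entry test counts, a negative baseline swab followed by a negative Day 3 swab is clearance, dated to the baseline swab. A swab on the day before dosing gives −1 + 1 = day 0; a swab on the dosing day gives 0 + 1 = day 1. Both come before any plausible drug effect.

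**Step 2: effect on the clearance difference.** Let p be the clearance proportion among baseline-detectable subjects.
- Never cleared: p becomes (1 − q)p.
- Cleared at once: p becomes q + (1 − q)p.

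In both cases the arm difference is (1 − q)(p1 − p2). With 60% v 50%, 10.0 points becomes 9.5, 9.0 and 8.0 at q = 5, 10 and 20%.

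**Step 3: power, two-sided 0.05.** Full mITT has 334 per arm. The restricted set has 334(1 − q) per arm but keeps the undiluted difference.

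| Clearance | q | mITT, never cleared | mITT, cleared at once | Restricted |
|---|---|---|---|---|
| 60% v 50% | 5% | 0.69 | 0.70 | 0.72 |
| 60% v 50% | 10% | 0.64 | 0.66 | 0.69 |
| 60% v 50% | 20% | 0.55 | 0.58 | 0.64 |
| 60% v 40% | 20% | 0.989 | 0.989 | 0.997 |

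**Step 4: sample-size factor against restriction.** With V = p1(1 − p1) + p2(1 − p2), computed on diluted or undiluted rates, the factor is [V diluted / (1 − q)²] ÷ [V undiluted / (1 − q)], that is, (V diluted / V undiluted) / (1 − q). For 60% v 50% at q = 20%, never cleared: V diluted = 0.48 × 0.52 + 0.40 × 0.60 = 0.4896 and V undiluted = 0.24 + 0.25 = 0.49, giving 0.4896 / 0.49 / 0.8 = 1.25. Cleared at once: 0.68 × 0.32 + 0.60 × 0.40 = 0.4576, giving 0.4576 / 0.49 / 0.8 = 1.17. At q = 5% the two factors are 1.06 and 1.04. For 70% v 50% at q = 20% they are about 1.3 and 1.15. The range is roughly 1.05 to 1.3.

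**Step 5: log10 change.** This was simulated with 1,000 trials of 668 subjects. Assumptions: baseline 6 (SD 1.5) log10, mean fall 2.0, treatment effect −0.4, residual SD 1.5, floor at log10(59.9) = 1.78. At q = 20%:

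| | Full mITT | Restricted |
|---|---|---|
| Estimated difference | −0.27 | −0.34 |
| t-test power | 0.67 | 0.83 |
| Baseline-adjusted power | 0.82 | 0.84 |

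The adjusted model was a single-visit ANCOVA; MMRM uses the same covariate but was not simulated.

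**Step 6: percent reduction and AUC.** Percent reduction has the baseline load in its denominator, so it is undefined at zero. For AUC, the SAP does not say whether a below-LoQ baseline counts as missing, so it is unclear whether such subjects drop out. SAP 4.11.4 has only a general line on turning character laboratory values into numbers; there is no rule specific to viral load.

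**The case against.** A reader might infer that the SAP scores these subjects as never cleared, or as cleared at once. It states neither. The definition does require a positive test; what is missing is that test's source and timing.

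A reader might also infer that every viral endpoint is diluted. The documents do not support that. ANCOVA and MMRM adjust for baseline, and in the simulation baseline adjustment recovers nearly all the power, though the estimate still shrinks. Percent reduction at zero baseline is undefined rather than diluted. AUC handling cannot be determined. mITT is named for the viral time-to-event analyses, but not expressly for the clearance proportions, log10 change or AUC.

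It is also tempting to put the loss at 1/(1 − q)², or 1.11 to 1.56. That compares full mITT with a full-size trial in which everyone is detectable. Restriction cannot deliver that, because it gives up the same q of subjects.

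Three further arguments have force. The share may be small, since entry needs symptoms within 5 days and a first positive within 3 days. Attenuation is towards the null, so it does not manufacture an efficacy claim. And full mITT is a defensible choice of estimand for a treated population. These points limit the size and rank of the concern. They do not remove the undefined positive test, or an event time of day 0 or 1.

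**Conclusion.** The concern holds in this form. The qualifying positive test for clearance is undefined, no detectable central baseline is required, and a subject undetectable throughout can be censored or counted as an event at day 0 or 1. Under either reading the clearance difference shrinks by (1 − q). The unadjusted t-tests on log10 change also lose power. The baseline-adjusted analysis keeps most of its power but reports a smaller effect.

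For an assumed q of 5–20%, the efficiency loss against a restricted analysis is about 1.05 to 1.3 times the sample. It matters for modest effects (60% v 50%) and is negligible for large ones (60% v 40%). The size rests on assumed values for q and for clearance; the ambiguity in the definition does not. The endpoints are secondary and the primary result is untouched. The change should be made, but the trial's main conclusion does not depend on it.

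**What to change.** In SAP 4.10.3:

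1. State that the qualifying positive for clearance is the central baseline ddPCR swab.
2. Run clearance, time to clearance, percent reduction and log10 change in mITT subjects whose central baseline is at or above the LoQ (59.9 copies/mL). Do the same for AUC.
3. State one below-LoQ rule for viral load, covering the value used on the log10 scale and whether a below-LoQ result counts as missing for AUC.
4. Report the number excluded by arm, and keep full mITT as supportive, with the scoring of baseline-undetectable subjects written out.

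The subset is fixed by a pre-dose measurement, so the randomized comparison within it is preserved. The cost is SAP wording and one baseline flag; the downside is fewer subjects in the main viral tables.
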